3.1 Problem of hyperkalemia

Patients with end stage renal disease (ESRD) who are treated with conventional hemodialysis (HD) schedules often exhibit life-threatening, episodic hyperkalemia. Reduced kidney function increases extracellular potassium concentration due to the combined effects of a net positive potassium balance in concert with disturbed ion distribution in the body fluid compartments ¹⁻². In the HD population, scheduled measurement of serum potassium concentration is typically performed only once or twice a month. Even with this restricted testing schedule, serum potassium exceeds 5 mEq/L in more than a third of patients ^{3,4}. However, episodes of hyperkalemia are likely much more common during conventional HD, since many of these transient events are not captured with standard treatment and testing schedules. Episodic hyperkalemia disrupts the electrophysiology of heart muscle and can promote cardiac arrhythmias. It is plausible that episodes of hyperkalemia contribute to the alarmingly high rate of sudden cardiac arrest, by far the most common cause of death in the HD population ^{5,6}. But consistent control of serum potassium levels is difficult in HD patients. Our own data suggest that 40-50% of HD patients who exhibit serum potassium concentrations > 5.5 mEq/L during routine measurements in one month will fail to be “cured” the following month with usual clinical care (unpublished data). One dilemma that arises is that reducing serum potassium with the use of low dialysate potassium is actually associated with an increased risk of sudden cardiac death ⁵. Furthermore, HD patients already carry a high pill burden, and it is unclear if prescription of an additional oral medication will reduce the frequency of episodic hyperkalemia ⁷. Even though the manner of achieving this ideal is unclear, these observations suggest that avoiding extremes in the concentrations of serum potassium will improve the cardiovascular risk in HD patients.

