High serum potassium contributes to cardiac risk. Maintaining serum potassium homeostasis is critical to create a stable transmembrane potential of about -85 mV, and this permits normal cardiac and skeletal muscle function ⁸. Abrupt changes in serum potassium levels result in deviations in membrane potential that can lead to muscle paralysis and to fatal arrhythmias ⁸. In patients with ESRD, the ability to maintain potassium balance by the kidney is diminished, and therefore acceptable potassium conditions can only be approximated by dietary potassium restriction and clearance with dialysis. In a patient maintained on a conventional, three-times-per-week HD regimen, potassium intake is recommended to be limited to about 60 mEq/day (420 mEq/week). Dialysis removal typically is around 70-100 mEq per treatment (210-300 mEq/week for thrice-weekly schedules)². Assuming that native kidney function accomplishes minimal potassium clearance, to maintain a near-steady potassium concentration potassium elimination through the gastrointestinal tract is essential.

In the general population, the normal range for serum potassium is typically reported between 3.5 and 5.0 mEq/L but in HD patients the ideal serum potassium concentration tends to be higher. In a study of 2,134 HD patients, a pre-dialysis serum potassium level of 5.1 mEq/L was associated with the lowest risk of peri-dialytic sudden cardiac arrest, while potassium levels above and below 5.1 were associated with increasing risk ⁵. Another study examining pre-dialysis serum potassium levels and survival within a cohort of 81,013 hemodialysis patients, potassium concentrations between 4.6-5.3 mEq/L were associated with the lowest incidence of all-cause mortality ⁹ and a survey of 55,183 HD patients in the Dialysis Outcomes and Practice Patterns Study (DOPPS) multinational cohort confirmed that the lowest risk of death was observed among patients with serum potassium levels between 4 and 5.5 mEq/L and a significant increased risk of death and arrhythmia outcomes at potassium values ≥ 5.6 mEq/L ¹⁰. In a study of serum potassium values obtained within a large dialysis organization, approximately 20% of all serum potassium measurements were ≥ 5.5 mEq, and about 12.5% of measurements were ≥ 6.0 , whereas potassium < 4.0 accounted for only 9% of all measurements ⁴.

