6.4. Consent

Patients will be provided the Informed Consent Form and this will be reviewed by the Study Personnel. Patients will be encouraged to take the form home and review with their family if possible

6.5 Baseline period, Week 0

Once a patient has signed the ICF, a 12 lead ECG will be obtained. The long term cardiac monitor will be placed at the end of HD3 prior to Week 0 and removed at the beginning of HD3 of Week 0. Weight, pulse, and blood pressure will be recorded. Medical history and demographic data will be collected. Medications will be recorded. The hemodialysis prescription for target weight and dialysate potassium and calcium will be recorded.

Before each hemodialysis session in Week 0, blood samples will be collected and sent to the clinical laboratory. The Renal Function Panel and magnesium levels will be determined with these samples before the first dialysis session of the week (HD1). Serum pregnancy test will be measured for females of child-bearing potential.

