6.6 Randomization

Randomization will occur at any time in Week 0 prior to HD3. This will be done using the REDCap system and will assign patients 1:1 to either continue usual care or to receive patiromer as detailed below.

6.7 Open-label patiromer and dose titration, Weeks 1, Week 2, Week 3, Week 4.

Patients randomized to the patiromer arm will initiate on 8.4 g/day (one pack) given once a day with breakfast or lunch, to start after HD3 at the end of Week 0. The patient is instructed to not take any other medications for three hours before or three hours after patiromer.

The patiromer dose will be titrated based on serum potassium concentrations on HD1 of weeks 1, 2, and 3. Patiromer will be increased by 8.4 g/day if $K \geq 5.5$ meq/L, decreased by 8.4 g/day if $K < 4.5$ mEq/L, and patiromer will be discontinued if $K < 4$ mEq/L.

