6.12 Concomitant medications

Except for those listed in the exclusion criteria, all medications (prescription or over-the-counter) initiated prior to enrollment may be continued during the course of the study.

All medications that are continued from the start of the study or that are started during the study (other than the study medication) including prescription or over-the-counter will be documented by the study team.

6.13 Follow-up evaluations Weeks 1, 2

A member of the study team will see the patient at the start of HD1 Week 1. Weight, pulse and blood pressure will be recorded. A pre-dialysis serum potassium lab sample will be collected and sent to the clinical lab. Concomitant medications will be recorded.

With study team visit on HD2 or HD3 of Week 1, the patiromer dose will be titrated based on the pre-dialysis potassium measured at HD1. Patiromer will be increased by 8.4 g/day if $K \geq 5.5$ meq/L, decreased by 8.4 g/day if $K < 4.5$ mEq/L, and patiromer will be discontinued if $K < 4$ mEq/L.

6.14 The assessment period Weeks 3, 4 and 6

A member of the study team will see the patient at the start of HD1 Week 3 and HD1 Week 4. Weight, pulse and blood pressure will be recorded. A pre-dialysis serum potassium lab sample will be collected and sent to the clinical lab to measure potassium. Concomitant medications will be recorded.

With study team visit on HD1 of Week 3, the patiromer dose will be titrated based on the pre-dialysis potassium measured at HD1. Patiromer will be increased by 8.4 g/day if $K \geq 5.5$ meq/L, decreased by 8.4 g/day if $K < 4.5$ mEq/L, and patiromer will be discontinued if $K < 4$ mEq/L.

The long term heart monitor (LTHM; Telepatch #2) will be placed at the end of HD3 Week 3 and removed at the beginning of HD3 of Week 4.

With study team visit on HD1 of Week 6, weight, pulse and blood pressure will be recorded. A pre-dialysis blood sample will be collected and sent to the clinical lab for a renal function panel. Concomitant medications will be recorded.

6.15. Withdrawal of subjects.

A subject may discontinue participation in the study at any time without being obligated to give a reason, although they are free to do so if they wish.

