8.1. Primary analysis

This is a proof-of-concept study, to determine the extent to which administration of patiromer has the potential to change the risk category for ESRD patients who are on conventional HD schedules. In addition, the study

aims to develop and test study procedures and instruments that will be implemented in a large-scale clinical trial.

By nature of the size of the study, the power of the trial will be limited for the primary analysis. The proposed primary endpoint is the between-group differences of the number of episodes, per subject, of serum K \geq 5.5 mEq/L during Weeks 3 and 4. This will be assessed as follows: Six serum samples will be collected and assessed for each patient during the efficacy phase (Weeks 3 and 4). Patients would receive a score of perfect K control (6 of 6 samples in range; Score 1.0), moderate K control (5 of 6 in range; Score 0.83), inconsistent K control (4 of 6 in range; Score 0.67), erratic K control (3 of 6 in range; Score 0.50), poor K control (2 of 6 in range; Score 0.33), very poor K control (1 of 6 in range; Score 0.17), or no K control (0 of 6 in range, Score 0). These scores will then be averaged for the patients in the active treatment group and the control group, and the results will be compared. Using this approach, a sample size of n=20 per group provides 86% power to detect a between-group difference of 2 in mean episodes of hyperkalemia per patient, assuming $\alpha=0.05$ and standard deviation 2.

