8.2 Secondary endpoints

Because study sample size is limited and is based only on the amount of information needed to adequately assess the primary hypothesis, this pilot study will have limited power to effects on secondary endpoints. We consider these measurements to be exploratory. A significant effect on the exploratory endpoints will be considered in light of the results of the primary analysis.

Differences in laboratory values between the treatment groups will be determined by analysis of variance (ANOVA). The long-term heart monitor results will be compared in the following ways:

Group 1: Individual patient compared by their LTHM #1 vs LTHM #2;

Group 2: Individual patient compared by their LTHM #1 vs LTHM #2

Group 1 LTHM #1 vs Group 2, LTHM #1;

Group 1 LTHM #2 vs Group 2, LTHM #2

Each monitor will be assigned a point score, counting only the most severe event.

Finding	Score
Sustained VT, VF and/or asystolic cardiac arrest (CPR required)	10
Nonsustained VT (\geq 3 beats but $<$ 30 seconds) and/or $>$ 5 second pause during daytime (0800-2000) and/or atrial fibrillation ($>$ 30 seconds)	3
PVC $>$ 1000/24h and/or $>$ 3 second pause during daytime (0800-2000)	2
PVC $>$ 500/24h and/or or HR $<$ 40 for 5 consecutive beats during daytime (0800-2000)	1

Monitor period scores will be tabulated, and differences in period scores addressed by ANOVA.

Heart rate variability will be recorded in time-domains from the LTHM and periods will be compared.

The QT intervals will be compared for the LTHM periods in two different procedures. The mean QTc will be determined for each 7 day period, and groups will be compared. In addition, in the LTHM will collect 30 second rhythm strips in the last dialysis session (HD3) of week 4, and QTc will be determined and compared between the treatment groups.

Bradyarrhythmias will be recorded and classified for comparison as follows: asystole > 5 seconds with syncope, third degree AV block, second degree AV block, sinus pause > 3 seconds, and sinus bradycardia < 40 bpm.

9. Monitoring

The sponsor of the study, Relypsa, will provide study monitoring at a mutually agreeable time, during normal business hours.

10.. Schedule of Assessments

Procedures/Visits	Pre- Week 0	Week 0			Week 1			Week 2			Week 3			Week 4		
		Visit	HD1	HD2	HD3	HD1	HD2									
Week		1		2		3		4		5						
Determination of Elevated K Episodes	X															
Informed Consent	X															
Medical History and Demography		X														

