Randomization ¹			X													
Initiation of Patiromer ²				X												
Patiromer titration ³					X			X				X		X		
Physical Exam		X														
Vital Signs ⁴ (BP, HR, Height, Weight)		X			X				X			X		X		X
Renal Function Panel		X														
Serum Potassium			X	X	X				X			X	X	X	X	X
Serum Magnesium		X							X			X				X
Serum Pregnancy Test ⁵		X														
Holter Monitor Applied	X															X
Holter Monitor Removed			X													
Previous medication and concomitant medication		X	X	X	X				X			X		X	X	X
Adverse Event Questioning		X	X	X	X				X			X		X	X	X
Dialysis ⁶																
ECG	X	←								→						

1=Randomization can occur at any point after Week 0 HD1 as long as it is completed prior to Week 0, HD3.

2=If randomized to the Patiromer Arm

3=Patiromer will be increased by 8.4 g/day if K \geq 5.1 mEq/L, decreased by 8.4 g/day if K<4.0 mEq/L, and discontinued if K<3.5mEq/L

4= Blood Pressure taken after sitting for 5 minutes; Height only collected at Week 0, HD1

5=Females of child bearing potential

6= Hemodialysis should be performed 3 times per week

BIBLIOGRAPHY

6. System USRD. 2017 USRDS annual data report: Epidemiology of kidney disease in the United States. Bethesda, MD: National Institutes of Health, National Institute of Diabetes and Digestive and Kidney Diseases; 2017.

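### The primary analysis makes no use of pre-randomisation Week 0 potassium; a prespecified ANCOVA would gain precision if baseline and outcome correlate above about 0.17

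*Combined protocol and SAP*

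**What the plan says.** Section 8.1 (repeated in the synopsis) defines the primary endpoint as the number of Week 3-4 samples per patient at or above 5.5 mEq/L, re-expressed as the fraction of six samples in range. The scores are then "averaged for the patients in the active treatment group and the control group, and the results will be compared". No test, model, covariate or sidedness is given. The power statement uses 20 per group, a difference of 2 episodes, SD 2 and alpha 0.05, and gives 86%.

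On baseline data, 6.5 says: "Before each hemodialysis session in Week 0, blood samples will be collected and sent to the clinical laboratory". The schedule in section 10 puts the Renal Function Panel at Week 0 HD1 and lists serum potassium separately at HD2 and HD3. No efficacy analysis uses any of these values; change from baseline appears only among the safety summaries.

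On timing, 6.6 says: "Randomization will occur at any time in Week 0 prior to HD3". Footnote 1 of the schedule is narrower: "Randomization can occur at any point after Week 0 HD1 as long as it is completed prior to Week 0, HD3". Patiromer starts after HD3 of Week 0 (6.7).

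For secondary laboratory endpoints, 8.2 says: "Differences in laboratory values between the treatment groups will be determined by analysis of variance (ANOVA"), again with no covariate.

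**The concern.** The protocol itself says that power for the primary analysis is limited. It makes no allowance for dropout, and 6.16 rules out replacing withdrawn patients. A pre-randomisation measurement of the variable behind the outcome is the cheapest source of extra precision, and the plan leaves it unused.

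Two further matters follow.

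- **Chance imbalance.** With 20 per arm and no stratification described, the baseline difference between arms has standard error sqrt(2/20) = 0.316 SD. A gap above 0.5 SD then occurs with probability of about 11%. At r = 0.5 such a gap moves the unadjusted estimate by 0.5 × 0.5 × 2 = 0.5 episodes, a quarter of the target difference. ANCOVA corrects for this.
- **Prespecification.** The trial is open-label. A covariate chosen after the data are seen, or measured after assignment is known, would be open to challenge. Under footnote 1 only HD1 always precedes assignment: HD2 may not, and HD3 never does. Under 6.6 read alone, no Week 0 draw is guaranteed to come first.

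**Working it through.** **Inputs.** From 8.1: n = 20 per arm, difference 2, SD 2, alpha 0.05. Two-sided testing is assumed, since the plan does not say. The correlation r is not in the documents, so a range is shown. The episode count equals 6 × (1 − score), so score and count give the same test.

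**The plan's own figure.** Two-sample t-test, 38 df, noncentrality 2 / (2 × sqrt(2/20)) = 3.162: power 86.9%, against 86% stated. A one-sided t-test would give 92.8%. The stated figure therefore matches an unadjusted two-sided comparison with the full SD. The 95% CI half-width is 2.024 × 2 × sqrt(2/20) = 1.28 episodes.

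**ANCOVA with one baseline covariate.** The residual SD is 2 × sqrt(1 − r²), with 37 df. Chance covariate imbalance multiplies the variance of the treatment effect by 1 + T²/38, with T distributed as t on 38 df. Its mean is 1 + 1/36 = 1.028. Power is averaged over T. Equivalent unadjusted n per arm is 20 / [(1 − r²) × 37/36].

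| Analysis | Power | 95% CI half-width | Difference detectable at 80% power | Equivalent n per arm |
|---|---|---|---|---|
| Unadjusted | 86.9% | 1.28 | 1.82 | 20 |
| ANCOVA, r = 0 | 85.9% | 1.30 | 1.84 | 19.5 |
| ANCOVA, r = 0.3 | 88.9% | 1.24 | 1.76 | 21.4 |
| ANCOVA, r = 0.5 | 93.9% | 1.13 | 1.60 | 25.9 |
| ANCOVA, r = 0.67 | 98.3% | 0.96 | 1.37 | 35.3 |

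Break-even is at r of about 0.17. The r = 0.67 row is an illustrative upper end. Direct simulation with normal data (20,000 trials) gave 86.0%, 88.6%, 94.0% and 98.4% for the four ANCOVA rows.

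**What the documents suggest about r.** Section 3.1 reports that "40-50% of HD patients who exhibit serum potassium concentrations > 5.5 mEq/L during routine measurements in one month will fail to be" cured the next month, and that "approximately 20% of all serum potassium measurements were" at or above 5.5 mEq/L. Taking 20% as the rate in both months, phi = (q − 0.20) / (1 − 0.20):

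- q = 0.40: 0.20/0.80 = 0.25, power 88.0%
- q = 0.50: 0.30/0.80 = 0.375, power 90.6%

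On a latent-normal scale the same figures give a correlation between single measurements of 0.44 to 0.61.

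**Bounded outcome.** The outcome is a 0-6 count, so linear ANCOVA is an approximation. A simulation with assumed latent-normal potassium, patient share of variance 0.5, HD1 as the only covariate, mean difference 2.0 and SD about 1.86 (6,000 trials) gave, unadjusted against ANCOVA:

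- r = 0: 89.3% against 88.5%
- r = 0.29: 88.9% against 90.8%
- r = 0.40: 89.2% against 92.9%
- r = 0.58: 88.5% against 97.4%

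The type I error of ANCOVA under the null was 4.5% to 5.5%.

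**Is HD1 potassium available?** At Week 6, 6.14 says: "A pre-dialysis blood sample will be collected and sent to the clinical lab for a renal function panel". No other laboratory test is named there, yet change in potassium two weeks after stopping drug is a secondary endpoint (4.2, item 8). The protocol therefore relies on this panel to report potassium, and the same panel is drawn at Week 0 HD1.

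**The case against.** The strongest reply is that this is an optional refinement. The unadjusted comparison is valid, planned power already exceeds 80%, the trial calls itself proof-of-concept, and adjustment loses power if r is below 0.17.

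The evidence on r is also weak. It combines unpublished persistence data with a rate from a different dialysis population, and one uses a strict inequality at 5.5 while the other does not. Neither describes the patients selected here. A phi between two single dichotomised readings is not the correlation of one continuous value with a six-sample count.

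Selection on high potassium at entry narrows the baseline range, and titration flattens the baseline-outcome slope in the treated arm. In a simulation with both built in (assumed latent-normal potassium, mean 5.0, SD 0.8, patient share of variance 0.3 to 0.5, effect 0.25 to 0.4 mEq/L per packet, 2,000 trials), r was 0.15 to 0.27 in the treated arm and 0.31 to 0.45 in controls.

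Much of this stands. The size of the gain is uncertain, the 93.9% and 98.3% figures should not be read as expected values, and slopes may differ by arm. It is also fair that 8.1 names no test, so that unadjusted is an inference, though the match to 86% supports it. Footnote 1 narrows 6.6 and does not contradict it. All Week 0 draws precede drug, so the difficulty with HD2 and HD3 is knowledge of assignment, not drug effect.

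None of this removes the point. In that simulation pooled r was 0.24 to 0.37 and ANCOVA gained about 1 to 6 points. A second simulation of the same kind gave pooled r of about 0.25 to 0.43 and gains of about 0.5 to 5 points, with a gain in every scenario.

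**Conclusion.** The concern holds as a conditional statement about efficiency. The plan gives pre-randomisation potassium no role in the primary analysis, and a prespecified ANCOVA would narrow the interval for any r above about 0.17. A realistic gain, on the documents' rough figures and with allowance for selection and titration, is from under one point to about six points of power. The possible loss is about one point (86.9% to 85.9%). Larger gains need r of 0.5 or more, which the documents do not establish.

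The figures assume 20 evaluable patients per arm, SD 2, two-sided alpha 0.05 and approximate linearity. Use of HD1 also assumes that the Renal Function Panel reports potassium, which the Week 6 endpoint implies. The conclusion that adjustment is worth prespecifying is firm; its exact benefit is not.

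**What to change.** - In 8.1, name the primary analysis: ANCOVA of the six-sample score (equivalently the episode count) on arm and Week 0 HD1 pre-dialysis potassium, or the mean of values drawn before randomisation. Test at two-sided 0.05 and report the adjusted difference with its 95% CI.
- Keep the unadjusted difference as a supportive analysis.
- Use the HD1-HD3 mean only as a sensitivity analysis, because HD3, and possibly HD2, follows open-label assignment.
- In 6.6, state that randomisation follows the HD1 draw, in line with footnote 1, and confirm that the HD1 panel potassium is recorded.
- In 8.2, apply the same adjustment to secondary laboratory values that have a Week 0 measurement.

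The cost is SAP wording, one sentence in 6.6, one degree of freedom, and about one point of power if r is near 0. No new patients, samples or visits are needed.

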8.2 Secondary endpoints

Because study sample size is limited and is based only on the amount of information needed to adequately assess the primary hypothesis, this pilot study will have limited power to effects on secondary endpoints. We consider these measurements to be exploratory. A significant effect on the exploratory endpoints will be considered in light of the results of the primary analysis.

Differences in laboratory values between the treatment groups will be determined by analysis of variance (ANOVA). The long-term heart monitor results will be compared in the following ways:

Group 1: Individual patient compared by their LTHM #1 vs LTHM #2;

Group 2: Individual patient compared by their LTHM #1 vs LTHM #2

Group 1 LTHM #1 vs Group 2, LTHM #1;

Group 1 LTHM #2 vs Group 2, LTHM #2

Each monitor will be assigned a point score, counting only the most severe event.

Finding	Score
Sustained VT, VF and/or asystolic cardiac arrest (CPR required)	10
Nonsustained VT (\geq 3 beats but $<$ 30 seconds) and/or $>$ 5 second pause during daytime (0800-2000) and/or atrial fibrillation ($>$ 30 seconds)	3
PVC $>$ 1000/24h and/or $>$ 3 second pause during daytime (0800-2000)	2
PVC $>$ 500/24h and/or or HR $<$ 40 for 5 consecutive beats during daytime (0800-2000)	1

Monitor period scores will be tabulated, and differences in period scores addressed by ANOVA.

Heart rate variability will be recorded in time-domains from the LTHM and periods will be compared.

The QT intervals will be compared for the LTHM periods in two different procedures. The mean QTc will be determined for each 7 day period, and groups will be compared. In addition, in the LTHM will collect 30 second rhythm strips in the last dialysis session (HD3) of week 4, and QTc will be determined and compared between the treatment groups.

Bradyarrhythmias will be recorded and classified for comparison as follows: asystole > 5 seconds with syncope, third degree AV block, second degree AV block, sinus pause > 3 seconds, and sinus bradycardia < 40 bpm.

9. Monitoring

The sponsor of the study, Relypsa, will provide study monitoring at a mutually agreeable time, during normal business hours.

10.. Schedule of Assessments

Procedures/Visits	Pre- Week 0	Week 0			Week 1			Week 2			Week 3			Week 4		
		Visit	HD1	HD2	HD3	HD1	HD2									
Week		1		2		3		4		5						
Determination of Elevated K Episodes	X															
Informed Consent	X															
Medical History and Demography		X														
Randomization ¹			X													
Initiation of Patiromer ²				X												
Patiromer titration ³					X			X				X		X		
Physical Exam		X														
Vital Signs ⁴ (BP, HR, Height, Weight)		X			X				X			X		X		X
Renal Function Panel		X														
Serum Potassium			X	X	X				X			X	X	X	X	X
Serum Magnesium		X							X			X				X
Serum Pregnancy Test ⁵		X														
Holter Monitor Applied	X															X
Holter Monitor Removed			X													
Previous medication and concomitant medication		X	X	X	X				X			X		X	X	X
Adverse Event Questioning		X	X	X	X				X			X		X	X	X
Dialysis ⁶																
ECG	X	←								→						

1=Randomization can occur at any point after Week 0 HD1 as long as it is completed prior to Week 0, HD3.

2=If randomized to the Patiromer Arm

3=Patiromer will be increased by 8.4 g/day if K \geq 5.1 mEq/L, decreased by 8.4 g/day if K<4.0 mEq/L, and discontinued if K<3.5mEq/L

4= Blood Pressure taken after sitting for 5 minutes; Height only collected at Week 0, HD1

5=Females of child bearing potential

6= Hemodialysis should be performed 3 times per week

BIBLIOGRAPHY

6. System USRD. 2017 USRDS annual data report: Epidemiology of kidney disease in the United States. Bethesda, MD: National Institutes of Health, National Institute of Diabetes and Digestive and Kidney Diseases; 2017.

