4.2 Secondary endpoints

1. To determine whether patiromer can effectively be used in place of one dose of phosphate binder per day
2. To determine the between-group differences in percent of patients with serum $K > 5.5$ mEq/L
3. To determine the efficacy and dosing of patiromer in ESRD patients.
4. To determine the between-group differences in need for additional hemodialysis treatments due to hyperkalemia
5. To determine the between-group differences in pre-specified significant arrhythmia events as detected with cardiac monitors in Week 4.
6. To determine the between-group differences in serum albumin and PTH concentrations.
7. To determine feasibility of a large-scale hemodialysis-based trial.
8. To determine the change in serum potassium concentration two weeks after study drug is discontinued
9. To determine the change in serum phosphorus concentration two weeks after study drug has been discontinued
10. To develop procedures and instruments to be employed in a large scale clinical trial.

5. Selection and withdrawal of subjects

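### Section 8.2 lists four heart-monitor comparisons with equal standing; only one tests treatment, and none adjusts for the baseline recording that every patient provides

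*Combined protocol and SAP*

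**What the plan says.** Secondary objective 5 (Section 4.2 and the synopsis) is a randomised comparison: "To determine the between-group differences in pre-specified significant arrhythmia events as detected with cardiac monitors in Week 4". The synopsis likewise has the monitor endpoints assessed between the two groups.

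Section 8.2 then lists four comparisons and ranks none of them:

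1. "Group 1: Individual patient compared by their LTHM #1 vs LTHM #2"
2. "Group 2: Individual patient compared by their LTHM #1 vs LTHM #2"
3. "Group 1 LTHM #1 vs Group 2, LTHM #1"
4. "Group 1 LTHM #2 vs Group 2, LTHM #2"

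The wording for the individual endpoints differs:

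- **Arrhythmia score:** "Monitor period scores will be tabulated, and differences in period scores addressed by ANOVA".
- **Heart rate variability (HRV):** "Heart rate variability will be recorded in time-domains from the LTHM and periods will be compared".
- **QTc:** two procedures. One takes the mean over each 7-day recording and compares the groups. The other compares strips from the last dialysis session of Week 4 between the treatment groups.

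On timing, Section 6.5 has LTHM #1 "removed at the beginning of HD3 of Week 0", and Section 6.7 starts patiromer after that session. Section 8.2 calls the secondary measurements exploratory, says power for them is limited, and says a significant result will be read in light of the primary analysis.

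**The concern.** A within-arm before/after test mixes any drug effect with everything else that changes between Week 0 and Week 4. Here that includes a second monitor wear and the dietary teaching and printed flyer given to all participants (Section 6.9). Two such tests side by side invite the inference that a significant change in one arm and a non-significant change in the other shows a treatment effect. It does not, because the difference between the arms has not been tested.

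The comparison of arms at LTHM #1 precedes dosing, so it says nothing about treatment.

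With no contrast named as the treatment test, the report could rest on whichever of the four is significant. The plan also leaves precision unused: each patient has a baseline recording, but no model adjusts for it, in a trial of about 20 per arm.

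**Working it through.** **Plan's own figure.** The only computed figure is power for the primary endpoint (Section 8.1): n = 20 per group, difference 2, SD 2, alpha 0.05, stated power 86%. The noncentrality is 2 / (2 × √(2/20)) = 3.16. A two-sided t test with 38 df then gives 86.9%, which agrees. This supports 20 per arm and two-sided 0.05 as working values. The plan gives no figure for the monitor comparisons.

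**What each comparison estimates**

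| Comparison | Type | Tests treatment? | Can a shared change make it significant? |
|---|---|---|---|
| Group 1, #1 vs #2 | within arm | no | yes |
| Group 2, #1 vs #2 | within arm | no | yes |
| #1, Group 1 vs 2 | between arms, before drug | no | no |
| #2, Group 1 vs 2 | between arms, on treatment | yes | no |

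Section 8.2 does not say which arm is Group 1. The list is symmetric, so this does not affect the count.

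**Chance of a misleading pattern.** Assumptions, none of them from the documents: paired t tests at two-sided 0.05, normal changes, no treatment effect, and the same shift d in both arms, in SDs of the within-patient change. Let p be the one-sample t power at n = 20. The arms are independent, so the chance that patiromer is significant and usual care is not equals p(1 − p).

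| d | p | p(1 − p) |
|---|---|---|
| 0 | 0.050 | 0.048 |
| 0.2 | 0.136 | 0.118 |
| 0.3 | 0.247 | 0.186 |
| 0.45 | 0.480 | 0.250 |
| 0.6 | 0.721 | 0.201 |

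The range is about 12% to 25%, against about 5% with no shift.

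**Check by simulation.** This used 40,000 replicates, 20 per arm, a shared shift of 0.5 SD of the outcome and before/after correlations of 0.3 to 0.7:

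- patiromer before/after test significant: 43% to 78%;
- patiromer significant and usual care not: 17% to 25%;
- LTHM #2 by arm, and the same comparison adjusted for LTHM #1: both about 5%.

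**Gain from adjustment.** Conditioning on a covariate with correlation r leaves a fraction 1 − r² of the variance. At r = 0.5 the reduction is 0.5² = 25%; at r = 0.7 it is 0.7² = 49%. The documents do not give r.

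**The case against.** The strongest reply is that the right test is already there. Comparison 4 is between arms on treatment, objective 5 and the synopsis are between-group, and the endpoints are labelled exploratory. The other three comparisons can be read as description. This stands, and it limits the point to a clarification. It does not remove the gap: Section 8.2 gives the four equal standing and still anticipates significant exploratory effects, and no label turns a before/after test into a test of treatment.

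Several stronger readings are tempting, but the documents do not support them:

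- **HRV is compared only between periods.** Its own sentence names only periods, but the four-way list governs LTHM results generally and HRV comes from the LTHM. The contrast is unclear, not absent.
- **QTc is equally exposed.** Both QTc procedures are written as group comparisons. QTc is exposed only through the general list.
- **All three non-treatment comparisons can turn positive from a shared change.** The LTHM #1 comparison cannot; it stays near 5%.
- **The ANOVA treats a patient's two recordings as independent.** The plan does not say so; the list speaks of individual patients, and ANOVA can include repeated measures. If pairing were ignored, standard errors would be 1/√(1 − r) times too large, or 1.4 to 1.8 times at r = 0.5 to 0.7. That makes the before/after tests conservative, so this figure cannot be combined with the paired-test figures above.
- **The risk is 24% to 50%.** That range, 2p(1 − p), counts significance in either arm alone. The pattern that would be credited to patiromer is half of it.
- **Multiple testing gives a 46% false-positive chance.** 1 − 0.95¹² = 0.46 requires 12 independent tests (four comparisons on three endpoints). The four comparisons reuse the same recordings.
- **These results will justify the large trial.** The plan speaks of testing procedures and instruments and of feasibility; it does not make the monitor results a decision input.

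One caution on the remedy: Section 6.6 lets randomisation fall while LTHM #1 is being worn. In an open-label trial that recording is pre-drug but not wholly pre-randomisation. Patiromer cannot have affected it, so it remains usable as a baseline.

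**Conclusion.** The point holds as a gap in specification. Of four monitor comparisons listed as equals, one tests treatment, and no contrast uses LTHM #1 as a covariate. The ambiguity is greatest for HRV and the arrhythmia score and least for QTc. A reader might infer that the plan lacks a between-group test or that its monitor results are invalid; neither follows, since comparison 4 is sound and planned.

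The 12% to 25% rests on 20 per arm with complete recordings, paired tests, normal changes and an assumed shared shift of 0.2 to 0.6 SD of change. The arrhythmia score is far from normal, so for that endpoint the figure is only indicative. The precision gain rests on an assumed correlation. Because the endpoints are exploratory and the change costs almost nothing, this is a free improvement.

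**What to change.** In Section 8.2:

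- Name LTHM #2 by randomised arm, adjusted for the same patient's LTHM #1 result, as the treatment comparison for the arrhythmia score, HRV and 7-day mean QTc.
- Use analysis of covariance for HRV and mean QTc. For the skewed 0/1/2/3/10 score, use a rank-based or ordinal version.
- Report LTHM #1 by arm and the within-arm changes in descriptive tables without p-values.
- Leave the Week 4 strip QTc comparison as it is; it is already between arms.

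The cost is a few sentences in Section 8.2. No new data, visits or recordings are needed, and the endpoints keep their exploratory status.
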